Opioid-free anesthesia (OFA) involving a combination of drugs and techniques was suggested to avoid opioids from intraoperative analgesia. It was intended to avoid opioid from the postoperative analgesia regimen but was later taken as a viable and optional method for perioperative anesthesia management([11](#), [12](#)). Individual medications such as N-methyl-D-aspartate (NMDA) antagonists, sodium channel blockers, anti-inflammatory drugs, and alpha-2 agonists are being administered for analgesia. They aimed to reduce the reduction of MAC of volatile anesthetics, avoiding negative effects associated with opiates, and providing greater patient satisfaction after surgery when used in combination ([13-18](#)).

Intravenous lidocaine in doses less than 2mg/kg is reported to relieve pain by blocking sodium channels in both the peripheral and central nervous systems. It was also thought to reduce central and deafferentation pain and aid in wound healing. At lower doses up to 1 mg/kg, ketamine can provide significant pain relief without negative effects by eliminating opioid tolerance and having anti-hyperalgesic effects. A combination of intravenous (IV) lidocaine and low-dose ketamine can be used for intraoperative analgesia without adverse effects, even though it has not been routinely used for intraoperative anesthesia.

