2.4. The effectiveness of drugs used in OFA

Wang et al., in the review of 12 randomized controlled studies comprising about 900 patients undergoing different surgical procedures under GA, compared s-ketamine in bolus doses of 0.075 to 0.5 mg/kg and infusions from 1.25 to 10 μ g/kg/min with placebo. They recorded better pain scores at rest up to 24 hours in patients given ketamine and similar pain scores at 48 hours postoperatively ($p = 0.53$) in both ketamine and placebo(41).

In another meta-analysis of nine randomized controlled trials comparing IV ketamine with placebo for adult surgical patients on opioid use, Forget et al also documented a significant decrease in postoperative pain scale at 24 hours in patients taking ketamine, with a mean difference of -0.79. About a 97 mg and 186 mg decrease in opiate consumption at 24 and 48 hours, respectively, were documented in patients taking ketamine (16).

In the review of recent works of literature on subanesthetic doses of ketamine for intraoperative pain and up to 48-hour postoperative administration, Jouguelet et al. reported a reduction of postoperative pain score and up to 40% reduction of postoperative analgesic consumption by bolus then continuous infusions given of up to 1.2 mg/kg/h or 1.3 mg/kg ketamine doses, respectively. On subanesthetic ketamine use, and reported that ketamine, when used in a subanesthetic dose, has no documented associated adverse events (42).

Touchier et al. performed an RCT by using lidocaine with ketamine on 36 gynecologic patients without dexmedetomidine and reported better hemodynamic stability in the OFA group ($p = 0.0026$) compared to opioid-based anesthesia with remifentanil (30).

Foo et al., in the statement on the efficacy and safety of lidocaine, described the analgesic, anti-hyperalgesic, and anti-inflammatory effects of lidocaine from its actions on muscarinic and NMDA receptors. They recommended 1–2 mg/kg as an initial bolus followed by a continuous infusion of 0.5–3 mg/kg/hr. Avoiding a dose greater than or equal to 3 mg/kg/hr, and avoiding lidocaine in patients with hepatic or renal impairment. Lidocaine should not be used on patients whose weight is less than 40 kg([12](#)).

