4.4.2. Exclusion criteria

Patients with allergies to any of the drugs used in the trial

Patients with chronic pain

Patients who are diagnosed with CNS diseases, like psychiatric diseases or epilepsy([46](#))

Patients who are hypertensive and taking beta-blockers, as well as those who have preoperative bradycardia, hypotension, or any type of heart block([47](#))

Patients weighing less than 40 kg or obese patients (BMI > 35 kg/m²)([12](#))

Patients with a history of smoking

Patients who are scheduled for postoperative mechanical ventilation

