4.8.1.2. Secondary outcome variables

- Postoperative analgesic requests between groups
- The occurrence of postoperative nausea and vomiting (PONV) between the groups
- The occurrence of intraoperative cardiac adverse events between groups

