4.10. Data collection procedures

After getting ethical clearance from the Dilla University College of Health Sciences and Medicine ethical review board, a structured questionnaire will be formed and translated into the respective languages by the principal investigator (PI). Two BSC anesthetists involved in patient management will be selected at both study areas and trained in the overall process of participant handling and data collection.

During the preoperative period

Patients undergoing gynecologic operations during the study period will be assessed and told about the study process and anesthetic the day before the surgery. The patient will receive maintenance fluid, had bilateral peripheral IV lines secured, and was NPO the night before surgery. On the morning of the procedure, both a standard informed consent form for the procedure and a separate consent form for the study will be checked and available.

The availability and functionality of the bilateral IV line, and NPO status will be checked, and prophylactic drugs will be given. Standard preoperative questionnaires will be used, and data will be collected through patient responses and medical records, such as patient monitoring and charts.

At intraoperative period

Routine ASA monitoring will be checked and applied for patients in both groups when the patient presented to the OR. The functionality and availability of the bilateral IV line and urinary catheter will be rechecked. Propofol (3 mg/kg) will be given to induce anesthesia after the patient had been pre-oxygenated for both groups. An intravenous bolus of 0.5 mg/kg of ketamine during the induction phase for patients in the treatment group, then a continuous infusion of 0.2 mg/kg/hr. Of ketamine. A bolus of 1.5 mg/kg will be given before induction, and the same dose of lidocaine will be administered every 15 to 20 minutes after induction of anesthesia until the start of skin closure.

Patients in the control group will be induced with fentanyl 2 μ g/kg given during induction of anesthesia with propofol 3mg/kg. 0.5 μ g /kg of fentanyl will be given every 20-30 minutes up to the start of skin closure.

Intubation will be performed after administering 1.5–2 mg/kg IV suxamethonium. Inhalational anesthetics as availabilities (Isoflurane 0.75–2% and Halothane 1%_ 2%) were opened after the position of the ETT was confirmed, and Dexamethasone 0.15mg/kg IV bolus will be given after securing the ETT.

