Anesthesia will be maintained with inhalational agents according to the patient's tidal volume of 6–8 ml/kg adjusted to maintain oxygen saturation >95% with 3- 4 ml 100% oxygen flow, and end-tidal CO₂ between 32 and 45 mmHg. Muscle relaxation will be maintained with vecuronium 0.8 mg/kg. Intraoperative anesthesia depth will be assessed by clinical signs as well as by patient monitoring. Estimated intraoperative blood loss will be supplied with ringer lactate or normal saline.

The intraoperative participants' data will be collected from the anesthesia record chart and patient monitoring. Intraoperative hemodynamic variables will be collected every 10 minutes. Intraoperative cardiac adverse events such as intraoperative bradycardia (pulse rate less than 50 bpm), tachycardia (PR greater than 100 bpm), hypertension, and hypotension we diagnosed and managed as per institutional protocol. Intraoperative nausea or vomiting in both groups will also be managed as an institutional protocol.

When the surgeon begins skin closure, the inhalational agent will be turned off. A pre-prepared reversal agent bolus (neostigmine 0.05 mg/kg with atropine 0.02 mg/kg IV) was administered for patients given long-acting muscle relaxants after checking the adequacy of spontaneous ventilation, adequate movement of the respiratory bag, oxygen saturation >95percentage and ETCO₂ between 32 and 45 mmHg after the skin is closed.

During the postoperative period

The postoperative pain severity will be assessed by the validated VAS starting from the patient's discharge from PACU to 24 hours postoperatively. Data will be collected at discharge from PACU, at 6 hours, 12 hours, and 24 hours postoperatively. Analgesia request at postoperative times will be recorded as the patient's request for analgesia according to the VAS score. PONV data will be collected from the time of arrival at PACU at 6 hours, 12 hours, and 24 hours postoperatively according to the patient's signs and symptoms.

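### Harm collection is thin in both arms and omits the ketamine-lidocaine regimen's own postoperative effects, so the trial can say nothing about CNS or postoperative cardiac harm

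*Combined protocol and SAP*

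**What the plan says.** **Outcomes.** Besides analgesic requests, section 4.8.1.2 lists PONV and "The occurrence of intraoperative cardiac adverse events between groups". Section 4.10 sets their windows. The cardiac outcome is "Intraoperative cardiac adverse events such as intraoperative bradycardia (pulse rate less than 50 bpm), tachycardia (PR greater than 100 bpm), hypertension, and hypotension". For the other, "PONV data will be collected from the time of arrival at PACU at 6 hours, 12 hours, and 24 hours postoperatively". Pain is scored at PACU discharge and at 6, 12 and 24 hours, so four postoperative contacts already exist. The only other item recorded after surgery is the request for analgesia.

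**Analysis.** Section 4.12 assigns a test to PONV (chi-square or Fisher) and none to the cardiac events.

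**Oversight.** Section 4.13 provides a three-person monitoring committee that looks into matters affecting participants and the conduct of the intervention. It has no event list, form or time window.

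**Background on harm.** Section 1.1 (Background) states: "A combination of intravenous (IV) lidocaine and low-dose ketamine can be used for intraoperative analgesia without adverse effects". Section 2.4 reports that "ketamine, when used in a subanesthetic dose, has no documented associated adverse events".

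**Lidocaine.** Section 4.10 gives 1.5 mg/kg before induction and the same dose again, "administered every 15 to 20 minutes after induction of anesthesia until the start of skin closure". Section 2.4 summarises a consensus statement that advises against 3 mg/kg/h or more.

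**The concern.** The trial adds two drugs to the treatment arm, and no stated outcome could show an effect of either drug on the CNS at any time, or on the heart once the operation ends. The one harm followed after surgery, PONV, is among the effects that the Background attributes to opioids.

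A report built on these outcomes could show less PONV in the treatment arm and no entry for that arm's own postoperative effects, because none were sought. Section 1.2 expects the result to influence patient management, so readers could mistake an unmeasured harm for an absent one. The Background sentence on adverse effects makes that mistake easier.

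**Working it through.** **Step 1. What is counted, and when** (sections 1.1, 4.8.1.2, 4.9, 4.10 and 4.12):

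| Harm | During surgery | PACU to 24 h | Test named in 4.12 |
|---|---|---|---|
| Bradycardia, tachycardia, hypertension, hypotension | Outcome, both arms | Not collected | None |
| Nausea and vomiting | Managed, not an outcome | Outcome, both arms | Chi-square or Fisher |
| Ileus, constipation (opioid effects named in 1.1) | Not collected | Not collected | None |
| Any CNS effect | Not collected | Not collected | None |
| Any other adverse event | Not collected | Not collected | None |

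The postoperative column has one filled row. The gap affects both arms: two opioid effects that the protocol names are also missing.

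**Step 2. The lidocaine passages side by side.** The average hourly rate of the repeat doses is the dose times the number of doses per hour:

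- every 20 minutes: 1.5 × 60/20 = 4.5 mg/kg/h
- every 15 minutes: 1.5 × 60/15 = 6.0 mg/kg/h

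Against the 3 mg/kg/h cited in section 2.4, these are 4.5/3 = 1.5 and 6.0/3 = 2 times the figure. Section 2.4 speaks of a continuous infusion and section 4.10 of repeated boluses, so this compares average rates only.

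**Step 3. What collection could show.** The plan gives no figure for harms. Its sample size (section 4.5) was set for pain: 31 per group, 62 in total, 70 after the 10% addition, hence 35 per arm.

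- Zero events in n treated patients give a one-sided 95% upper bound of 1 − 0.05^(1/n). For n = 35 this is 8.2%; for n = 31 it is 9.2%. The upper limit of the two-sided exact 95% interval for 0/35 is 1 − 0.025^(1/35) = 10.0%.
- The chance of seeing no event at true rate p is (1 − p)^35: 17% at p = 5%, 49% at p = 2%, 70% at p = 1%.
- To bring the one-sided bound below 5% with zero events takes ln 0.05 / ln 0.95, rounded up to 59 treated patients. Below 1% takes 299.
- Between arms of 35, Fisher's exact test gives p = 0.054 for 5 versus 0 events and p = 0.025 for 6 versus 0. Its power is 33% for 20% versus 5%, and 13% for 10% versus 0%. These rates are assumptions; the documents give none.

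For harms that are not recorded, none of these quantities can be stated.

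**The case against.** The strongest reply is that safety is not what this trial tests. The hypotheses and the general objective concern pain, no safety conclusion is planned, and 35 patients per arm could not establish safety however carefully harms were recorded. The one opioid-free safety signal the protocol cites, severe bradycardia in a stopped trial (Problem statement), is covered: bradycardia belongs to a secondary outcome and has a numeric threshold. All of this stands. It limits the point to what the trial may conclude and does not remove it.

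Several stronger readings are tempting, and the documents do not support them:

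- *Collection is tilted toward opioid-free anesthesia by design.* Both listed harms are compared between arms, and ileus and constipation are missing too. PONV is no assured advantage: section 2.2 cites a gynecologic trial with 71.4% versus 70.5%. Section 1.2 also gives a neutral reason for measuring it, the PONV risk of gynecologic surgery.
- *The trial rests on the regimen having no adverse effects.* That is a Background sentence, not a hypothesis or objective, and section 1.2 acknowledges reports of drug-related side effects.
- *The exclusion of "Patients who are diagnosed with CNS diseases, like psychiatric diseases or epilepsy" shows that the protocol sees a CNS risk from these drugs.* Section 4.4.2 gives no reason, and reliable self-report of pain is another possible one.
- *CNS effects could appear only after emergence.* The first lidocaine bolus precedes induction.
- *The stopped trial shows that the intraoperative window is wrong.* The protocol does not say when its bradycardia occurred, and the reference list shows that it used dexmedetomidine.

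Finally, the structured questionnaire is not in the available text and Annex One has no content there, so further items cannot be ruled out. If they exist, sections 4.8.1.2, 4.10 and 4.12 should name them.

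**Conclusion.** The point holds in a limited form. On the stated outcomes, the trial can describe PONV to 24 hours and cardiac events during surgery. It can say nothing about CNS harm or postoperative cardiac harm of the ketamine-lidocaine regimen, and so can neither support nor refute the Background statement on adverse effects. The average lidocaine rate, 1.5 to 2 times a figure the protocol itself cites, makes the missing data more important. Sections 2.4 and 4.10 must be reconciled on this; the documents do not settle which governs.

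Collecting the data would move the trial from no bound at all to an upper bound of about 8% if no event occurred (35 patients observed; about 9% with 31). A reader should not infer that this would demonstrate safety. The primary pain comparison is unaffected. The conclusion assumes that the missing annex holds no further harm items.

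**What to change.** 1. At the existing PACU-discharge, 6, 12 and 24 hour contacts, add a short yes/no adverse-event checklist, asked identically in both arms. Include CNS effects, with items chosen by the clinical investigators, and the opioid effects that section 1.1 names. Effects between the first lidocaine bolus and induction would still be missed, and the report should say so.
2. Extend the existing cardiac event count through PACU discharge, using the PACU chart. The text gives numeric limits only for the two pulse-rate events, so state how hypertension and hypotension are defined and use the same definitions in both windows.
3. Add these items and their analysis to sections 4.8.1.2 and 4.12: counts by arm with exact confidence intervals, presented as descriptive.
4. Limit any safety statement to the harms and windows collected.
5. Reconcile the lidocaine passages in sections 2.4 and 4.10.

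The cost is slightly longer contacts, extraction from the PACU chart and one more table, with no new visits or staff. The limitation is precision: at 35 per arm the data would inform but could not settle the safety question.

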4.2. Study design

A multi-centered, randomized, controlled, single-blinded trial will be conducted at Dilla University General and Teaching Hospital and Hawassa University Comprehensive and Specialized Hospital.

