4.7. Allocation concealment and blinding

Participants will be given a sealed envelope with the letter of the study group name in it and will be allowed to present it to the OR. Anesthesia providers involved in patient management will be allowed to know the drugs given and groups due to differences in anesthesia techniques, ethical issues, and patient diversity. Apart from patient management, the anesthetist will not be involved in any other study processes. Only participants assigned to groups will not know which group they will be selected for.

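### Hypotension and hypertension, two of the four named intraoperative cardiac events, have no numeric criterion and are diagnosed by providers who know the arm, although readings are taken every 10 minutes.

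*Combined protocol and SAP*

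**What the plan says.** Section 4.8.1.2 lists as a secondary outcome "The occurrence of intraoperative cardiac adverse events between groups", and section 3.2 makes it a specific objective. Section 4.10 (intraoperative period) names four examples. Two have numbers: "bradycardia (pulse rate less than 50 bpm), tachycardia (PR greater than 100 bpm". The other two do not; the sentence ends "hypertension, and hypotension we diagnosed and managed as per institutional protocol". Neither the operational definitions (4.9) nor the exclusion criteria (4.4.2), which use hypotension as a criterion, give a blood-pressure value.

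The raw material for a definition is planned: "Intraoperative hemodynamic variables will be collected every 10 minutes", and intraoperative "data will be collected from the anesthesia record chart and patient monitoring". No rule turns readings into events. Section 4.12 assigns a chi-square or Fisher test to PONV; it mentions neither cardiac events nor a site term.

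On setting and blinding, the "trial will be conducted at Dilla University General and Teaching Hospital and Hawassa University Comprehensive and Specialized Hospital" (section 4.2), and section 4.7 states "Anesthesia providers involved in patient management will be allowed to know the drugs given and groups" and "Only participants assigned to groups will not know which group they will be selected for".

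**The concern.** A blood-pressure event without a threshold is whatever the person at the bedside calls one. Here that person knows whether the patient received ketamine and lidocaine or fentanyl, and may expect different hemodynamic behavior from each. If that expectation changes how readily an episode is labelled, the arms will differ in recorded events even when their blood pressures do not. Randomization does not protect against this, because the error arises after allocation and depends on it.

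The second issue is lesser. Two hospitals are involved, and no common institutional protocol is cited or reproduced. If their criteria differ, the same reading could count at one site and not at the other.

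At stake is the trial's stated comparison of intraoperative cardiac events, in its blood-pressure components and in any composite that includes them.

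**Working it through.** The plan states no figure for this outcome, so there is none to reproduce. The check is a comparison of the text, followed by an illustration of scale.

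**Text**

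| Component | Criterion in 4.10 | Can be derived from readings as written? |
|---|---|---|
| Bradycardia | below 50 bpm | yes |
| Tachycardia | above 100 bpm | yes |
| Hypertension | institutional protocol | no |
| Hypotension | institutional protocol | no |

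Who records events is unclear. Section 4.7 says the managing anesthetist has no study role beyond patient care. Section 4.10 selects anesthetists who manage patients and trains them in data collection. On either reading the intraoperative diagnosis is made by someone who knows the arm, and no blinded assessor is described.

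**Illustration 1: judgement that differs by arm**

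Inputs: 35 per arm (Executive Summary) and a 0.05 threshold (4.12). Assumed: the true event rate p, equal in both arms; the detection proportions s1 and s2; and an uncorrected two-sided Pearson chi-square test, since 4.12 names no test for this outcome. Rejection probabilities come from exact binomial enumeration.

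False difference = p × (s1 − s2). For example, 0.30 × (0.90 − 0.70) = 0.06.

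| True rate in both arms | Chance of p<0.05, full detection in both | 90% vs 70%: false difference | Chance of p<0.05 | 95% vs 60%: false difference | Chance of p<0.05 |
|---|---|---|---|---|---|
| 20% | 4.9% | 4 points | 7.5% | 7 points | 12.9% |
| 30% | 5.1% | 6 points | 8.6% | 10.5 points | 17.3% |
| 40% | 4.8% | 8 points | 11.3% | 14 points | 24.8% |
| 50% | 4.3% | 10 points | 13.3% | 17.5 points | 32.2% |

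With the milder assumption of 90% versus 80%, the false difference is 2 to 5 points and the chance of p<0.05 is 5.6% to 6.7%.

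Over-labelling works the same way. If 10% of non-events are called events in one arm only, a true 30% becomes 0.30 + 0.70 × 0.10 = 0.37, against 0.30 in the other arm.

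For comparison, the standard error of a difference at 30% is √(2 × 0.30 × 0.70 / 35) = 0.11, or 11 points. The 6-point and 7-point shifts are about 0.5 and 0.6 of that.

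**Illustration 2: criteria that differ by site**

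Under 1:1 randomization the expected arm bias is zero. Section 4.6 mentions no stratification by site, so chance imbalance remains. Assume 35 patients from each hospital and criteria that produce event rates 25 points apart. By the hypergeometric distribution, the SD of one site's share within an arm is √(35 × 0.5 × 0.5 × 35/69) / 35 = 0.060. The two arms' shares move in opposite directions, so the SD of their difference is 2 × 0.060 = 0.120. The chance arm difference at 1.96 SD is 1.96 × 0.120 × 25 = about 6 points.

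**The case against.** The strongest reply is that this is a missing detail in one loosely worded sentence. Grammatically, the reference to institutional protocol covers all four events, and it describes diagnosis and management without saying how outcome events will be counted. The data come from charts and monitors, and section 4.7 keeps the managing anesthetist out of other study processes. A definition could also sit in the questionnaire or the annex, neither of which can be seen.

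Part of this stands. The documents do not establish that unblinded anesthetists do the counting, because 4.7 and 4.10 conflict on that. But the bedside diagnosis is open-label either way, and nothing visible directs anyone to derive blood-pressure events from the readings instead. If a definition exists in a form, it belongs in the protocol text.

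A reader might infer three stronger things that the documents do not support:

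- **That the hospitals use different criteria.** The text refers to institutional protocol in the singular and reproduces none. A difference is possible, not shown, and by itself would not favor an arm in expectation.
- **That the whole cardiac outcome is uninterpretable.** Bradycardia and tachycardia have cut-offs. The opioid-free trial stopped for severe bradycardia, cited in the problem statement, therefore does not bear on the missing threshold.
- **That 10-minute readings miss brief episodes equally in both arms.** Bolus intervals differ by arm (4.10: 15 to 20 minutes versus 20 to 30), and providers who know the group may treat before the next reading.

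**Conclusion.** The point holds for hypotension and hypertension. As written, two of the four named components of a secondary outcome depend on open-label judgement with no numeric criterion in the visible text, and this can bias the arm comparison. Site differences, if there are any, would add noise or chance imbalance. Bradycardia and tachycardia are not affected by a missing threshold, though the words introducing the list leave it open to other events.

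The size is unknown. The false differences of 2 to 17.5 points rest wholly on assumed event rates and detection, and the roughly 6 points of chance imbalance rests on an assumed 25-point gap between sites. With mild differential detection the effect on false-positive risk is small; with strong differential detection it is not. A composite that includes the heart-rate events could dilute it. Because the outcome is secondary and the remedy cheap, this should be corrected, but it does not threaten the primary pain comparison.

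**What to change.** For outcome counting only:

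1. Derive all four events at both hospitals from the recorded 10-minute values. Use the stated 50 and 100 bpm cut-offs and one numeric definition each of hypotension and hypertension, chosen by the investigators and fixed before data are seen by arm. A definition relative to baseline is feasible, since 4.8.2 lists preoperative hemodynamic variables. Confirm that the 10-minute set includes blood pressure, which 4.10 does not itemize.
2. Run the derivation without the group label.
3. Record treated episodes separately and report them alongside the derived events, because treatment between readings can hide an event and may do so differently by arm.
4. State the test for cardiac events and how site is handled in 4.12.
5. Reconcile 4.7 and 4.10 on whether the managing anesthetists collect data.

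Clinical management of events stays with the hospitals.

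The cost is a few sentences in the plan, a derived variable and one extra field for treated episodes. The downside is that brief episodes between readings are missed, not necessarily equally in both arms; step 3 reduces this but does not remove it, since the decision to treat is itself open-label.
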